6.3.2. Week 6 (Visit 5)

At Week 6 \pm 7 days relative to Day 1 (V4), subjects will return to the site after a minimum **10-hour fast** (except water) for V5. At this visit, the following procedures will be completed:

- Update concomitant medications since last visit.
- Assess treatment compliance with investigational product and counsel subject for non-compliance, as needed.
- Measure body weight in duplicate [refer to [Section 7.2](#)].
- Obtain duplicate orthostatic blood pressure and pulse rate measurement (supine \rightarrow standing) [refer to [Section 7.4.3](#)].
- Collect triplicate measurements of sitting blood pressure and pulse rate [refer to [Section 7.4.2](#)].
- Conduct inquiry about any spontaneously reported AEs by asking the subjects to respond to a non-leading question such as “how do you feel?” Assess potential clinical events for adjudication [refer to [Section 7.6](#)].
- Diet and exercise monitoring (see [Section 6.1.2](#)).
- Review self-monitoring blood glucose and Hypoglycemia Assessment Logs completed by the subject [refer to [Section 7.4.6](#)].
- Obtain blood and urine specimens for clinical laboratory tests [refer to [Section 7.4.1](#)] of:
 - Chemistry, urine pregnancy test (for women of childbearing potential) [refer to [Section 7.1](#)], HbA1c and FPG.
 - Pharmacokinetics of ertugliflozin (on a plasma sample) [refer to [Section 7.5.1](#)] including collection of date/time of blood draw and date/time of last dose of investigational product. PK sample is to be collected approximately 24 hr following the prior day's dose and before administration of the current day's dose.

Following completion of the above procedures:

- Provide subject with glucose meter supplies and additional self-monitoring blood glucose or hypoglycemia assessment logs, as needed.
- Contact IVRS.
- Dispense glimepiride glycemic rescue therapy, if applicable.
- Dispense investigational product.

6.3.3. Week 12 (Visit 6)

At Week 12 \pm 7 days relative to Day 1 (V4), subjects will return to the site after a minimum **10-hour fast** (except water) for V6. At this visit, the following procedures will be completed:

- Update concomitant medications since last visit.
- Assess treatment compliance with investigational product and counsel subject for non-compliance, as needed.
- Measure body weight in duplicate [refer to [Section 7.2](#)].
- Collect triplicate measurements of sitting blood pressure and pulse rate [refer to [Section 7.4.2](#)].
- Conduct inquiry about any spontaneously reported AEs by asking the subjects to respond to a non-leading question such as “how do you feel?” Assess potential clinical events for adjudication [refer to [Section 7.6](#)].
- Review self-monitoring blood glucose and Hypoglycemia Assessment Logs completed by the subject [refer to [Section 7.4.6](#)].
- Diet and exercise monitoring [refer to [Section 6.1.2](#)].
- Obtain blood and urine specimens for:
 - Clinical laboratory tests [refer to [Section 7.4.1](#)] including chemistry, hematology, urine pregnancy test (for women of childbearing potential) [refer to [Section 7.1](#)], HbA1c and FPG.
 - Pharmacokinetics of ertugliflozin (on a plasma sample) [refer to [Section 7.5.1](#)] including collection of date/time of blood draw and date/time of last dose of investigational product. PK sample is to be collected approximately 24 hr following the prior day's dose and before administration of the current day's dose.
 - The dose of double-blind investigational product should be administered and witnessed in clinic [refer to [Section 5.3.4](#)], time of administration should be collected.

Following completion of the above procedures:

- Provide subject with glucose meter supplies and additional self-monitoring blood glucose or hypoglycemia assessment logs, as needed.
- Collect a PK sample 1 h after dose administration of double-blind investigational product for ertugliflozin/placebo (with an allowable time window up to 3 hours post dose).
- Contact IVRS.

- Dispense glimepiride glycemic rescue therapy, if applicable.
- Dispense investigational product.

6.3.4. Week 18 (Visit 7)

At Week 18 \pm 7 days relative to Day 1 (V4), subjects will return to the site after a minimum **10-hour fast** (except water) for V7. At this visit, the following procedures will be completed:

- Update concomitant medications since last visit.
- Assess treatment compliance with investigational product and counsel subject for non-compliance, as needed.
- Measure body weight in duplicate [refer to [Section 7.2](#)].
- Collect triplicate measurements of sitting blood pressure and pulse rate [refer to [Section 7.4.2](#)].
- Conduct inquiry about any spontaneously reported AEs by asking the subjects to respond to a non-leading question such as “how do you feel?” Assess potential clinical events for adjudication [refer to [Section 7.6](#)].
- Review self-monitoring blood glucose and Hypoglycemia Assessment Logs completed by the subject [refer to [Section 7.4.6](#)].
- Diet and exercise monitoring (see [Section 6.1.2](#)).
- Obtain blood and urine specimens for clinical laboratory tests [refer to [Section 7.4.1](#)] of:
 - Chemistry, urine pregnancy test (for women of childbearing potential) [refer to [Section 7.1](#)], HbA1c and FPG;
 - Pharmacokinetics of ertugliflozin (on a plasma sample) [refer to [Section 7.5.1](#)] including collection of date/time of blood draw and date/time of last dose of investigational product. PK sample is to be collected approximately 24 hr following the prior day's dose and before administration of the current day's dose.
 - The dose of double-blind investigational product should be administered and witnessed in clinic [refer to [Section 5.3.4](#)], time of administration should be collected.

Following completion of the above procedures:

- Provide subject with glucose meter supplies and additional self-monitoring blood glucose or hypoglycemia assessment logs, as needed.

- Collect a PK sample 1 h after dose administration of double-blind investigational product for ertugliflozin/placebo (with an allowable time window up to 3 hours post dose).
- Contact IVRS.
- Dispense glimepiride glycemic rescue therapy, if applicable.
- Dispense investigational product.

6.3.5. Week 26 (Visit 8) – Final Study Visit / Early Termination Visit

At Week 26 \pm 7 days relative to Day 1 (V4), subjects will return to the site after a minimum **10-hour fast** (except water) for V8. At this visit (or early termination visit), the following procedures will be completed:

- Contact IVRS.
- Assess treatment compliance with investigational product.
- Review and update concomitant medications since last visit.
- Measure body weight in duplicate [refer to [Section 7.2](#)].
- Obtain supine, single, standard, 12-lead ECG [refer to [Section 7.4.4](#)].
- Collect triplicate measurements of sitting blood pressure and pulse rate [refer to [Section 7.4.2](#)].
- Conduct brief physical examination which includes assessment of heart, lungs, abdomen and extremities.
- Obtain duplicate orthostatic blood pressure and pulse rate measurement (supine \rightarrow standing [refer to [7.4.3](#)].
- Conduct inquiry about any spontaneously reported AEs by asking the subjects to respond to a non-leading question such as “how do you feel?” Assess potential clinical events for adjudication [refer to [Section 7.6](#)].
- Review self-monitoring blood glucose and Hypoglycemia Assessment Logs completed by the subject [refer to [Section 7.4.6](#)].
- Diet and exercise monitoring (see [Section 6.1.2](#)).

- Obtain blood and urine specimens for clinical laboratory tests [refer to [Section 7.4.1](#)] of:
 - Hematology, chemistry, urinalysis, urinary albumin/creatinine ratio, urine pregnancy test (for women of childbearing potential) [refer to [Section 7.1](#)], lipid panel, HbA1c, FPG;
 - Pharmacokinetics of ertugliflozin (on a plasma sample) [refer to [Section 7.5.1](#)] including collection of date/time of blood draw and date/time of last dose of investigational product. PK sample is to be collected approximately 24 hr following the prior day's dose.

Subjects, who discontinue from the trial prematurely, should be reminded that they will be contacted via telephone by the Investigator/qualified designee according to the same schedule as if they were still taking investigational product and will be asked to return for a visit at the Week 26 visit unless they withdraw consent per [Section 6.6](#).

6.4. Follow-up Phone Call

Each randomized subject should have a follow-up phone call 14 days after the last dose of investigational product to assess for AEs, SAEs and collect information on clinical events per [Section 7.6](#), if applicable. The phone call should be completed within a ± 3 day window.

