5.3.4. Administration of Double-Blind Investigational Product

On Day 1, each subject will be randomly assigned to ertugliflozin 5 mg, ertugliflozin 15 mg, or placebo.

The trial utilizes a double-dummy approach to maintain double-blinding, with a placebo tablet matching the ertugliflozin 5 mg tablet and another placebo tablet matching the ertugliflozin 10 mg tablet. Subjects will be dispensed 2 bottles and given clear dosing instructions. They will be instructed to take 2 tablets per day of double-blind investigational product, one from each bottle, as follows. Subjects randomized to ertugliflozin 5 mg will receive 1 ertugliflozin 5 mg tablet and 1 placebo ertugliflozin 10 mg tablet per day. Subjects randomized to ertugliflozin 15 mg will receive 1 ertugliflozin 5 mg tablet and 1 ertugliflozin 10 mg tablet per day. Subjects randomized to placebo will receive 1 placebo ertugliflozin 5 mg tablet and 1 placebo ertugliflozin 10 mg tablet per day.

The investigational product should be taken orally at approximately the same time of day in the morning from Day 1 through to Week 26 (last dose taken the morning prior to the Week 26 visit) or early termination. In addition, subjects will be instructed to delay the self-administration of investigational product on the day of their visits, when the visit assessments should be completed prior to administration. On Day 1, Week 12 and Week 18 visit days, subjects will take the dose of double-blind investigational product in the clinic after visit assessments.

If a subject misses a dose of investigational product during the trial, he/she should be instructed to take it as soon as the subject remembers unless it is time for the next dose. Subjects should be instructed not to "make up" for the missed dose by taking two doses at the same time.

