6. STUDY PROCEDURES

For the procedures described below, where multiple procedures are scheduled at the same time point(s) relative to dosing, the following chronology of events should be adhered to, where possible:

- *12-lead ECG*: obtain prior to vital signs assessment, blood samples, and prior to dosing.
- *Vital Signs (blood pressure and pulse rate)*: obtain after 12-lead ECG collection but prior to obtaining blood samples and prior to dosing.
- *Fasting blood and urine samples*: prior to dosing but after assessment of 12-lead ECG, and vital signs.
- *Other procedures*: all other procedures may be performed before or after blood specimen collection.
- Visit windows for this trial are recommended, not required.
- On scheduled visits to the site, subjects must be instructed to arrive without having taken the dose of investigational product, open-label metformin, or rescue therapy (if applicable). Other medications may be administered prior to the clinic visit if they can be administered without food. Subjects may eat to break their fast after the collection of weight, completion of laboratory procedures and blood pressure and pulse rate per the schedule of activity.

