The criteria to define clinical cardiovascular events will be detailed in the Endpoint Adjudication Committee charter. All potential clinical cardiovascular events will be collected from the first day of double-blind treatment through the end of study (including 14 day post-dose reporting period) for all randomized subjects who have received at least one dose of investigational product. The collection period will continue through study completion/end-of-study whether or not the subject continues to receive investigational product unless the subject is unwilling to be contacted by the personnel at the investigational site (ie, withdraws consent).

Clinical cardiovascular events occurring between the Screening visit (the time of informed consent) and double-blind treatment randomization will not be adjudicated as that subject will be excluded from the trial as per [Section 4.2](#).

The identification of a potential clinical cardiovascular event will be made by the trial site or by the Pfizer or designee. The site will communicate the event to Pfizer or designee within 24 hours of awareness of the potential clinical cardiovascular event using the appropriate CRF module. Pfizer or designee will in turn provide a listing of specific documents needed to support adjudication by the EAC. Obtaining documentation will be the responsibility of the trial site. Documentation will include, but is not limited to any of the following: hospital discharge summaries, operative reports, clinic notes, ECGs, diagnostic cardiac enzymes, results of other diagnostic tests, autopsy reports and death certificate information. The adjudication charter will contain additional information on source documents to be collected for event adjudication.

The composite of adjudicated events of cardiovascular death, non-fatal myocardial infarction, non-fatal stroke (often referred to as major cardiovascular events [MACE]), plus hospitalization for unstable angina will contribute to a meta-analysis of cardiovascular safety of ertugliflozin across the Phase 2 and 3 programs. Events of venous thromboembolism/pulmonary embolism and hospitalized congestive heart failure (CHF) will be separately tabulated across the Phase III clinical development program, and are not included in the cardiovascular composite of MACE plus hospitalized unstable angina.

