8. ADVERSE EVENT REPORTING

8.1. Assessing and Recording Adverse Events

An adverse event is defined as any untoward medical occurrence in a patient or clinical investigation subject administered a pharmaceutical product and which does not necessarily have to have a causal relationship with this treatment. An adverse event can therefore be any unfavorable and unintended sign (including an abnormal laboratory finding, for example), symptom, or disease temporally associated with the use of a medicinal product or protocol-specified procedure, whether or not considered related to the medicinal product or protocol-specified procedure. Any worsening (ie, any clinically significant adverse change in frequency and/or intensity) of a preexisting condition that is temporally associated with the use of the Sponsor's product, is also an adverse event.

Changes resulting from normal growth and development that do not vary significantly in frequency or severity from expected levels are not to be considered adverse events.

Examples of this may include, but are not limited to, teething, typical crying in infants and children and onset of menses or menopause occurring at a physiologically appropriate time.

Sponsor's product includes any pharmaceutical product, biological product, device, diagnostic agent or protocol-specified procedure, whether investigational (including placebo or active comparator medication) or marketed, manufactured by, licensed by, provided by or distributed by the Sponsor for human use.

Adverse events may occur during the course of the use of the Sponsor's product in clinical trials or within the follow-up period specified by the protocol, or prescribed in clinical practice, from overdose (whether accidental or intentional), from abuse and from withdrawal.

Adverse events may also occur in screened subjects during any pre-allocation baseline period as a result of a protocol-specified intervention, including washout or discontinuation of usual therapy, diet, placebo treatment or a procedure.

All adverse events will be recorded from the time the consent form is signed through 14 days following cessation of treatment and at each examination on the Adverse Event case report forms/worksheets.

8.2. Definition of an Overdose for This Protocol and Reporting of Overdose to the Sponsor

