8.4. Immediate Reporting of Adverse Events to the Sponsor

8.4.1. Serious Adverse Events

A serious adverse event is any adverse event occurring at any dose or during any use of Sponsor's product that:

- Results in death;
- Is life threatening;
- Results in persistent or significant disability/incapacity;
- Results in or prolongs an existing inpatient hospitalization;
- Is a congenital anomaly/birth defect;
- Is a cancer;
- Is associated with an overdose;
- Is an other important medical event.

Refer to [Table 6](#) for additional details regarding each of the above criteria.

Any serious adverse event, or follow up to a serious adverse event, including death due to any cause that occurs to any subject from the time the consent is signed through 14 days following cessation of treatment, whether or not related to the Sponsor's product, must be reported within 24 hours to Pfizer or designee either by electronic media or paper. Appropriate contact information can be found in the Investigator Trial File Binder (or equivalent).

Additionally, any serious adverse event, considered by an Investigator who is a qualified physician to be related to the Sponsor's product that is brought to the attention of the Investigator at any time outside of the time period specified in the previous paragraph also must be reported immediately to Pfizer or designee.

All subjects with serious adverse events must be followed up for outcome.

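### The follow-up call may be made from Day 11 after the last dose, but safety events are to be recorded through Day 14, so up to 3 days may pass without active questioning, chiefly in completers

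*Combined protocol and SAP*

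**What the plan says.** **Contact.** Section 6.4: "Each randomized subject should have a follow-up phone call 14 days after the last dose of investigational product". It continues: "The phone call should be completed within a ± 3 day window". The Schedule of Activities shows ±3 days in the call column, and its footnote on the call repeats 14 ± 3 days.

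**Collection period.** Section 8.1: "All adverse events will be recorded from the time the consent form is signed through 14 days following cessation of treatment". Section 8.4.1 sets the same period for SAEs, "from the time the consent is signed through 14 days following cessation of treatment". Section 7.6.1 collects potential cardiovascular events "through the end of study (including 14 day post-dose reporting period) for all randomized subjects" who took at least one dose.

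**Last dose in completers.** Section 5.3.4: "last dose taken the morning prior to the Week 26 visit". The Schedule lists no contact after that visit other than the call.

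**Status of windows.** Section 6: "Visit windows for this trial are recommended, not required". The Schedule places the ±3 days for the call in its row of recommended windows.

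**Scope of the call.** Section 6.4 has the call cover AEs, SAEs and clinical events for adjudication. The Schedule footnote on the call and Section 6.6 name only SAEs and the adjudicable or clinical events.

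**The concern.** The call is the means by which the site asks a completer about the post-treatment period. Its nominal day is the last day of that period, so half of a symmetric tolerance lies before the period ends. A site can follow every instruction, call on Day 11, and never be told to ask about Days 12 to 14. No section requires a second contact when the call is early.

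What is at stake is the completeness of post-treatment safety data: AE and SAE counts in this trial, and the adjudicated cardiovascular events that Section 7.6.1 sends to the programme-wide meta-analysis.

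**Working it through.** The plan states no figure for this point, so there is none to reproduce. The check is a day count.

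**Inputs**
- Nominal call day 14, window ±3 days (Section 6.4; Schedule of Activities). Earliest call = 14 − 3 = Day 11; latest = 14 + 3 = Day 17.
- Collection ends on Day 14 (Sections 8.1 and 8.4.1; Section 7.6.1 includes the same 14 days).
- Convention used here: the day of the call counts as covered.

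**Formula.** Days without active questioning = max(0, 14 − call day).

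| Call day | Days not asked about | Share of 14 days |
|---|---|---|
| 11 | 3 | 3/14 = 21.4% |
| 12 | 2 | 2/14 = 14.3% |
| 13 | 1 | 1/14 = 7.1% |
| 14 to 17 | 0 | 0% |

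**Average loss.** The documents give no distribution of call days, so the mean gap can lie anywhere from 0 days (every call on Day 14 or later) to 3 days (every call on Day 11). For illustration only, with calls spread evenly over Days 11 to 17:
- share of calls before Day 14 = 3/7 = 43%;
- mean gap = (3 + 2 + 1)/7 = 0.86 day per subject called.

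**Scale against the whole observation period.** Double-blind treatment plus follow-up is 26 × 7 + 14 = 196 days. The worst case is 3/196 = 1.5%; the illustrative mean is 0.86/196 = 0.4%.

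**Who is exposed**
- *Completers:* no later contact is scheduled, so the gap applies to all event types.
- *Early discontinuers who stay in follow-up:* Section 6.6 schedules further telephone contacts up to Week 26, and Section 6.6.1 asks them back for a Week 26 visit. Section 6.6 gives the purpose of the telephone contacts as SAEs and adjudicable events. Those events on Days 12 to 14 can usually still be picked up, so mainly non-serious AEs are exposed.
- *Those who stop in about the last two weeks:* Week 26 falls no later than Day 14 after their last dose (26 − 24 = 2 weeks), so they may have no later contact and resemble completers.

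**The case against.** The strongest reply is that an early call releases nobody from reporting. Section 8.4.1 requires any SAE through Day 14 to be reported within 24 hours, related or not, whenever the call took place. Section 7.6.1 continues cardiovascular event collection to the end of the study. Completers are also asked about AEs in clinic at Week 26, after their last dose. The target is Day 14 and ±3 days is a tolerance, so calls may cluster at the target and the mean gap may be well below 0.86 day.

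All of this stands, and it limits the point. A reader might infer that an early call closes the subject, or that events on the last days are never ascertained. The documents do not say so. What is lost is active questioning, and what remains is passive: the site must happen to learn of the event. That is a weak substitute for SAEs and weaker still for non-serious AEs.

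A second reply is that windows are only recommended. This does not close the gap. If it applies to the call, 3 days is the largest gap inside the window and not a strict limit. It does mean that a new window alone would be no more binding than the present one.

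**Conclusion.** The mismatch is real and small. A compliant call on Day 11, 12 or 13 leaves 3, 2 or 1 of the 14 required days without active questioning. The gap is complete for subjects who finish Week 26 and, for most early discontinuers still followed, largely confined to non-serious AEs.

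Two stronger readings are tempting and unsupported. One is that all of the approximately 495 randomized subjects are affected: only those called before Day 14 are, and discontinuers are partly covered by later contacts. The other is that 43% of calls will be early: that figure rests wholly on an assumed even spread over Days 11 to 17.

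The window is the same in all three double-blind arms, so the consequence is incomplete ascertainment, with no reason to expect bias between arms. The Week 26 efficacy analysis is not affected. The documents give no event rates from which to estimate missed events. The change is worth making because it is cheap, not because the likely loss is large.

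**What to change.** 1. In Section 6.4, the call column of the Schedule of Activities and the Schedule footnote on the call, replace ±3 days with +3 days, so that the call falls on Day 14 to Day 17. By the formula above, every call in that window leaves 0 days uncovered.
2. State that the call asks about all AEs, SAEs and adjudicable events through Day 14.
3. Because windows are only recommended, require a repeat call whenever contact was made before Day 14.
4. Align the scope of the call in the Schedule footnote and Section 6.6 with Section 6.4. Otherwise a site that follows the footnote need not ask about non-serious AEs even on Day 14.

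**Cost.** Wording changes only, with no added visit or procedure. The calling window narrows from 7 days to 4, and a site that calls early will occasionally have to call again.
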